9.2 Infections

Incidence of any TEAE infection will be provided, as well as a frequency distribution to describe the type of infection (e.g., bacterial/viral/fungal). These will also be provided in a by-subject listing.

9.3 Myeloid and Platelet Engraftment

Per protocol, “Myeloid engraftment will be defined as the first of 3 consecutive days when the absolute neutrophil counts (ANC) exceeds $0.5 \times 10^9/L$ and platelet engraftment will be defined as the first of 3 consecutive days when the platelet count exceeds $20 \times 10^9/L$ without transfusion support.”

The time to ANC engraftment will be calculated based on the date recorded in the CRF by the sites (calculated as: Date of ANC Recovery minus Initial RGI-2001 Infusion date). Engraftment times (using the first date for each subject) will be summarized using continuous methods among those who engraft, and the median time to ANC engraftment will be estimated as the time that the cumulative incidence estimate of the probability of engraftment reaches or exceeds $0.5 \times 10^9/L$.

Similar tabulated analyses will be presented for time of platelet recovery/engraftment.

9.4 Vital Signs

Vital signs including systolic and diastolic blood pressure (BP), body temperature, heart rate, and respiratory rate were to be obtained within 15 minutes prior to RGI-2001 infusion and were to be repeated within 30 minutes after the infusion. These will be summarized in a table and provided in a by-subject listing.

9.5 Karnofsky Performance Status

The Karnofsky Performance Status (scale ranging from 0-100) is collected at screening and at various timepoints throughout the Treatment and Follow-Up Periods, as indicated in the schedule of events in the protocol. This score will be summarized at baseline and Day 60, with change from baseline to Day 60. The analysis will be performed using continuous methods. All data, including other timepoints besides Day 60 will be provided in a by-subject listing.

9.6 Evaluation of Laboratory Parameters

Chemistry, hematology, urinalysis, coagulation and other laboratory parameters will be collected at screening and various timepoints throughout the treatment and follow-up periods, as indicated in the schedule of events in the protocol.

Local laboratories were used for all laboratory assessments. Laboratory testing, results, and normal ranges were provided by local laboratories. Out-of-range values (i.e., “low”, “normal”, or “high”) will be derived by the Sponsor’s database using the normal ranges provided by the individual local laboratories. Descriptive statistics by visit for laboratory parameters will be provided including change from baseline; these summaries will be based on SI units since each local laboratories may record values using different units.

In addition, for selected parameters, shift tables from baseline and figures of the values over time will be provided. For these selected parameters, if applicable, grading will be assigned using CTCAE version 5.0 guidelines (Appendix A) and summary tables will be provided.

9.7 Evaluation of Donor/Host Chimerism

Chimerism (method, cell source, number of donor cells and percent donor cells) will be presented in a by-subject listing.

9.8 Evaluation of Other Safety Parameters

Physical Exam and Urine Pregnancy Test were to be performed or measured at the scheduled timepoints as indicated in the schedule of events in the protocol. A by-subject listing will be provided for each of them.

Pharmacokinetic, pharmacodynamics and biomarker endpoints (as described in Protocol Sections 9.3.2-9.3.4) will be analyzed outside the scope of this SAP; separate reports will be created, as needed.

10.0 CONVENTIONS FOR CALCULATIONS AND TABULATIONS

Table 10.0 Conventions for Calculations and Tabulations

CONVENTION	DESCRIPTION
Age calculation	Age is derived within the database; it will not be calculated in SAS (Statistical Analysis Software). It is calculated as an integer in years as the difference between the subject's date of informed consent and the date of birth.
Baseline	Baseline is defined as the last assessment completed prior to the administration of the study drug on Day 0, (which also corresponds to date of transplant), unless specified otherwise.
Study Day	Date of visit or evaluation – date of first administration of RGI-2001. Per protocol, the first dose will be administered on Day 0.
Percentage calculation	Percentages are calculated as 100 x (numerator/denominator). Rounding is not necessary because rounding is handled by the display format. Denominator is the total number of subjects in a column group unless otherwise specified.
AE counting: general summary	In summary displays, AEs are counted only once per subject within a category (e.g., overall and preferred term).
AE counting: summary by assessment	When AEs are summarized within levels of another AE assessment (e.g., causality or severity), AEs are counted once per subject at the worst level of the assessment (e.g., least complementary relationship or greatest severity).
Change from Baseline	Current visit value – baseline visit value
Percent Change from Baseline	$100 \times ((\text{current visit value} - \text{baseline visit value}) / \text{baseline visit value})$

11.0 SPECIFICATIONS FOR ANALYSIS DISPLAYS

All headers, titles, footnotes, and footers specified in the table and listing shells will be displayed in the produced output. Notes to the programmer will not be included in the produced output. Any minor deviation will not necessitate a revision to the Statistical Analysis Plan (SAP) nor will it be considered a deviation from planned analyses. Only major differences in the analysis methods or

data handling will necessitate such documentation. The shells of tables and listings will be provided in a separate document from this SAP.

11.1 Format

All analysis displays will be created by using statistical and summarization procedures in SAS®, Version 9.4 or later, using a line size of 132 and a page size of 50. All margins of all tables and listings will be a minimum of 0.8 inch.

All displays are intended to be printed in landscape layout unless otherwise specified.

At the top of each table/listing, a number followed by the title will be presented. After the title line, a sub-title or population information may be presented. Horizontal lines will appear before and after the column heading of the table/listing. Footnotes will be under the main body of the table or listing display.

The sponsor’s name, protocol number, status of the output (i.e., draft or final), SAS program name, and the date and time of creation will be on the output. The page number will appear on the upper right corner of each output (Page X of Y).

Also included will be the source of the data (SDTM module for Listings, and Listing number for Tables).

Conventions for Tables

Tables will be delivered to the sponsor in Microsoft Word, Times New Roman, 10-point font. If necessary for formatting, an alternate font type or size may be used. The conventions for the analysis displays are shown in Table 11.1.1.

Table 11.1.1 Conventions for Tables

CONVENTION	DESCRIPTION
Decimals for summary statistics	General Rule: Relative to the number of decimals in the original data, 1 more decimal for the mean, median, and percentiles, 2 more decimals for standard deviation (SD) will be displayed, and the same number for minimum, maximum, and/or range. The maximum number of decimals will be 4. Some lab parameters or other data may require judicious deviation from this rule. Wherever possible, data will be decimal aligned.
Decimals and format for percentages	Unless otherwise specified, frequency tabulations will be presented by number and percentage, with the percentage in parentheses following the number. Percentages will be displayed to 1 decimal. A count of zero will exclude any percentage

	display. The ‘%’ will not follow the percentage value if ‘n (%)’ is displayed in the column header.
--	---

Conventions for Listings

Listings will be delivered to the sponsor in Microsoft Word, Courier New, 8-point font. If necessary for formatting, an alternate font type or size may be used. The conventions for the listings are shown in Table 11.1.2 and apply for each listing where relevant.

Table 11.1.2 Conventions for Listings

CONVENTION	DESCRIPTION
Population	All enrolled subjects will be included unless otherwise specified.
Subject Number	Subject numbers will be displayed as site number – subject number (XX-XXX).
Dates	Date information in the listing will use the date9. format (i.e., 01JAN2011) where possible. Otherwise, date formats will be displayed as recorded on the eCRF.
Unknown	‘U’ will represent ‘Unknown’ in date variables and categorical variables unless otherwise specified on the eCRF.
Missing Values	Missing values will be listed as represented in the clinical database (e.g., blanks, ‘NR’ for not reported).
Variable Units	In the listings, a unit associated with a variable will be presented within parentheses in the column label.
Visit Description	A visit column will be provided with the visit label and an adjacent column with the corresponding date of evaluation, if available. Screening will be the label for screening visits.
Sort Order	All listings will be sorted by subject number, followed by the visit date (if available), then by collection date (if available), then time (if available), or in the case of AEs and medications, start date followed by stop date.

11.2 Summary Tables to Be Provided

Table 11.2 Summary Tables

Table Number and Title	Analysis Population
Table 14.1.1: Subject Disposition (All Subjects)	All
Table 14.1.2: Deaths	Safety Analysis
Table 14.1.3: Subject Enrollment by Site	Safety Analysis
Table 14.1.4: Major Protocol Deviations	Safety Analysis
Table 14.1.5: Demographics	Safety Analysis
Table 14.1.6: Study Disease Characteristics	Safety Analysis
Table 14.1.7: Donor Characteristics (Safety Population)	Safety Analysis
Table 14.1.8: Conditioning Regimen (Safety Population)	Safety Analysis
Table 14.1.9: RGI-2001 Treatment Exposure (Safety Population)	Safety Analysis
Table 14.1.10: Concomitant Medications (Safety Population)	Safety Analysis
Table 14.1.11: Concomitant Medications Given as Acute GvHD Prophylaxis (Safety Population)	Safety Analysis
Table 14.1.12: Systemic Steroids and Other Therapies Given for Treatment of GvHD (Safety Population)	Safety Analysis
Table 14.2.2.1: Acute GVHD Incidence (Safety Population)	Safety Analysis
Table 14.2.2.2: Chronic GVHD Incidence (Safety Population)	Safety Analysis
Table 14.2.2.3: Acute GVHD by Organ by Stage by Keystone Criteria - Incidence (Safety Population)	Safety Analysis
Table 14.2.2.4: Acute GVHD by Organ by Stage by MAGIC Criteria - Incidence (Safety Population)	Safety Analysis
Table 14.2.2.5: Acute GvHD-Free Survival (GFS) using Keystone Criteria (Safety Analysis Population)	Safety Analysis
Table 14.2.2.6: Non-Relapse Mortality (NRM) (Safety Analysis Population)	Safety Analysis
Table 14.2.2.7: GvHD-Free, Relapse-Free survival (GRFS) (Safety Analysis Population)	Safety Analysis
Table 14.2.2.8: Overall Survival (OS) (Safety Analysis Population)	Safety Analysis
Table 14.2.2.9: Relapse-Free survival (RFS) (Safety Analysis Population)	Safety Analysis
Table 14.2.2.10: Time to Myeloid Engraftment (Safety Analysis Population)	Safety Analysis
Table 14.2.2.11: Time to Platelet Engraftment Criteria (Safety Analysis Population)	Safety Analysis
Table 14.2.3: Karnofsky Performance Status – Observed and Change from Baseline (Safety Population)	Safety Analysis
Table 14.3.1.1: Summary of Treatment-Emergent Adverse Events (Safety Population)	Safety Analysis
Table 14.3.1.2: Treatment-Emergent Adverse Events - Incidence by SOC and Preferred Term (Safety Population)	Safety Analysis
Table 14.3.1.3: Serious TEAEs – Incidence by SOC and Preferred Term (Safety Population)	Safety Analysis

Statistical Analysis Plan

REGiMMUNE Corporation

Protocol: RGI-2001-003

Table Number and Title	Analysis Population
Table 14.3.1.4: Related TEAEs – Incidence by SOC and Preferred Term (Safety Population)	Safety Analysis
Table 14.3.1.5: Serious and Related TEAEs – Incidence by SOC and Preferred Term (Safety Population)	Safety Analysis
Table 14.3.1.6: Grade 3 or 4 TEAEs – Incidence by SOC and Preferred Term (Safety Population)	Safety Analysis
Table 14.3.1.7: Grade 3 or 4 TEAEs and Related – Incidence by SOC and Preferred Term (Safety Population)	Safety Analysis
Table 14.3.1.8: Grade 5 TEAEs – Incidence by SOC and Preferred Term (Safety Population)	Safety Analysis
Table 14.3.1.9: Grade 5 TEAEs and Related – Incidence by SOC and Preferred Term (Safety Population)	Safety Analysis
Table 14.3.1.10: TEAEs occurring in $\geq 20\%$ of Subjects– Incidence by SOC and Preferred Term (Safety Population)	Safety Analysis
Table 14.3.1.11: TEAEs – Incidence by SOC and Preferred Term, and Worst Grade (Safety Population)	Safety Analysis
Table 14.3.1.12: Grade 3 or 4 TEAEs – Incidence by SOC, Preferred Term, and Worst Grade (Safety Population)	Safety Analysis
Table 14.3.1.13: Grade 3 or 4 TEAEs and Related – Incidence by SOC, Preferred Term, and Worst Grade (Safety Population)	Safety Analysis
Table 14.3.1.14: TEAEs occurring in $\geq 20\%$ of Subjects– Incidence by SOC, Preferred Term, and Worst Grade (Safety Population)	Safety Analysis
Table 14.3.1.15: TEAEs Leading to RGI-2001 Dose Interruption or Reduction – Incidence by SOC, Preferred Term, and Worst Grade (Safety Population)	Safety Analysis
Table 14.3.1.16: TEAEs Leading to Discontinuation of RGI-2001 – Incidence by SOC, Preferred Term, and Worst Grade (Safety Population)	Safety Analysis
Table 14.3.1.17: TEAEs Leading to Discontinuation from the Study – Incidence by SOC, Preferred Term, and Worst Grade (Safety Population)	Safety Analysis
Table 14.3.1.18: TEAEs with Dose-Limiting Toxicity – Incidence by SOC, Preferred Term, and Worst Grade (Safety Population)	Safety Analysis
Table 14.3.1.19: Infection TEAEs – Incidence by SOC, Preferred Term, and Worst Grade (Safety Population)	Safety Analysis
Table 14.3.1.20: TEAEs – Incidence by Preferred Term (Safety Population)	Safety Analysis
Table 14.3.1.21: Related TEAEs – Incidence by Preferred Term (Safety Population)	Safety Analysis
Table 14.3.1.22: Serious TEAEs – Incidence by Preferred Term (Safety Population)	Safety Analysis
Table 14.3.1.23: Grade 3 or 4 TEAEs – Incidence by Preferred Term (Safety Population)	Safety Analysis
Table 14.3.1.24: Grade 3 or 4 TEAEs and Related – Incidence by Preferred Term (Safety Population)	Safety Analysis

Statistical Analysis Plan

REGiMMUNE Corporation

Protocol: RGI-2001-003

Table Number and Title	Analysis Population
Table 14.3.1.25: Grade 5 TEAEs – Incidence by Preferred Term (Safety Population)	Safety Analysis
Table 14.3.1.26: Grade 5 TEAEs and Related – Incidence by Preferred Term (Safety Population)	Safety Analysis
Table 14.3.1.27: TEAEs occurring in $\geq 20\%$ of Subjects– Incidence by Preferred Term (Safety Population)	Safety Analysis
Table 14.3.1.28: TEAEs Leading to RGI-2001 Dose Interruption or Reduction – Incidence by Preferred Term (Safety Population)	Safety Analysis
Table 14.3.1.29: TEAEs Leading to Discontinuation of RGI-2001 – Incidence by Preferred Term (Safety Population)	Safety Analysis
Table 14.3.1.30: TEAEs Leading to Discontinuation from the Study – Incidence by Preferred Term (Safety Population)	Safety Analysis
Table 14.3.1.31: TEAEs with Dose-Limiting Toxicity – Incidence by Preferred Term (Safety Population)	Safety Analysis
Table 14.3.1.32: Treatment-Emergent Infections by Type (Safety Population)	Safety Analysis
Table 14.3.5.1: Serum Chemistry Laboratory Values – Observed and Change from Baseline (Safety Population)	Safety Analysis
Table 14.3.5.2: Hematology Laboratory Values – Observed and Change from Baseline (Safety Population)	Safety Analysis
Table 14.3.5.3: Coagulation Laboratory Values – Observed and Change from Baseline (Safety Population)	Safety Analysis
Table 14.3.5.4: Urinalysis Laboratory Values – Observed and Change from Baseline (Safety Population)	Safety Analysis
Table 14.3.5.5: ECG Parameter Values – Observed and Change from Baseline (Safety Population)	Safety Analysis
Table 14.3.5.6: Vital Sign Values – Observed and Change from Baseline (Safety Population)	Safety Analysis
Table 14.3.5.7: Hematology Laboratory Values Worsening from Baseline Grade 0-2 to Grade 3-4 During the Treatment-Emergent Period (Safety Population)	Safety Analysis
Table 14.3.5.8: Serum Chemistry Laboratory Values Worsening from Baseline Grade 0-2 to Grade 3-4 During the Treatment-Emergent Period (Safety Population)	Safety Analysis
Table 14.3.5.9: Shifts in Hematology Laboratory from Baseline During the Treatment-Emergent Period (Safety Population)	Safety Analysis
Table 14.3.5.10: Shifts in Serum Chemistry Laboratory from Baseline During the Treatment-Emergent Period (Safety Population)	Safety Analysis

11.3 Listings to Be Provided

Listings are numbered considering the ICH guidance.

Table 11.3 Listings

Listing Number and Title	Analysis Population
Listing 16.2.1 Study Completion	All Subjects
Listing 16.2.2 Protocol Deviations	All Subjects
Listing 16.2.3 Eligibility	All Subjects
Listing 16.2.4.1 Demographics	All Subjects
Listing 16.2.4.2 Height and Weight	Safety
Listing 16.2.4.3 Medical History	Safety
Listing 16.2.4.4 Initial Disease Status and Evaluation Prior to HSCT	Safety
Listing 16.2.4.5 Prior Therapies	Safety
Listing 16.2.4.6 HLA Typing and Donor Information	Safety
Listing 16.2.4.7 ECG	Safety
Listing 16.2.5.1 AlloHSCT Product Manipulation Methods	Safety
Listing 16.2.5.2 AlloHSCT Administration	Safety
Listing 16.2.5.3 Study Drug RGI-2001 IV infusion Administration	Safety
Listing 16.2.6.1 ANC and Platelet Recovery	Safety
Listing 16.2.7.1 Adverse Events	Safety
Listing 16.2.7.2 Serious Adverse Events	Safety
Listing 16.2.7.3 Dose-Limiting Toxicities	Safety
Listing 16.2.7.4 AEs Leading to Study Discontinuation	Safety
Listing 16.2.7.5 AEs Leading to Study Drug Interruption, Reduction, or Discontinuation	Safety
Listing 16.2.7.6 AEs Leading to Death	Safety
Listing 16.2.7.7 List of Serious Adverse Events (Part 2)	Safety
Listing 16.2.7.8 Infections	Safety
Listing 16.2.8.1 Laboratory Results – Serum Chemistry	Safety
Listing 16.2.8.2 Laboratory Results - Hematology	Safety
Listing 16.2.8.3 Laboratory Results - Coagulation	Safety
Listing 16.2.8.4 Laboratory Results - Urinalysis	Safety
Listing 16.2.8.5 Laboratory Results – Microscopic Urinalysis	Safety
Listing 16.2.8.6 Laboratory Results – Viral Tests	Safety
Listing 16.2.8.7 Serum Pregnancy Test	Safety
Listing 16.2.9 Preparative Regimen	Safety
Listing 16.2.10 PK Blood Draw	Safety
Listing 16.2.11 Blood samples for Immunophenotyping and Exploratory Studies	Safety
Listing 16.2.12 Molecular Diagnostics	Safety

Listing Number and Title	Analysis Population
Listing 16.2.13 Physical Exam	Safety
Listing 16.2.14 Assessments of aGvHD and cGvHD	Safety
Listing 16.2.15 Dates for aGVHD and cGVHD	Safety
Listing 16.2.16 aGvHD Assessments Keystone Criteria	Safety
Listing 16.2.17 aGvHD Assessments MAGIC Criteria	Safety
Listing 16.2.18 cGvHD Development and Maximum Grade since Last Report	Safety
Listing 16.2.19 Karnofsky Performance Status (KPS)	Safety
Listing 16.2.20 Chimerism	Safety
Listing 16.2.21 Disease Status (Part A)	Safety
Listing 16.2.22 Disease Status (Part B)	Safety
Listing 16.2.23 Concomitant Medications Given for GvHD Prophylaxis	Safety
Listing 16.2.24 Concomitant Medications – Other Than Those Given for GVHD Prophylaxis	Safety
Listing 16.2.25 Concomitant Procedures	Safety
Listing 16.2.26 Vital Signs	Safety
Listing 16.2.27 AlloHSCT Product Analysis	Safety
Listing 16.2.28 Lising for Time-to-Event Analyses	Safety
Listing 16.2.29 Acute GvHD via Keystone Criteria: Lising for Time-to-Event Analyses	Safety
Listing 16.2.30 Acute GvHD via MAGIC Criteria: Lising for Time-to-Event Analyses	Safety
Listing 16.2.31 Chronic GvHD: Lising for Time-to-Event Analyses	Safety
Listing 16.2.32 Dates for aGVHD and cGVHD	Safety
Listing 16.2.33 Dates for Outcomes	Safety

11.4 Figures to Be Provided

Table 11.4 Figures

Figure Number and Title	Analysis Population
Figure 1.1 Hemoglobin by Study Day Scatter Plot	Safety
Figure 1.2 Leukocytes by Study Day Scatter Plot	Safety
Figure 1.3 Lymphocytes by Study Day Scatter Plot	Safety
Figure 1.4 Neutrophils by Study Day Scatter Plot	Safety
Figure 1.5 Platelets by Study Day Scatter Plot	Safety
Figure 1.6 BUN by Study Day Scatter Plot	Safety
Figure 1.7 Creatine by Study Day Scatter Plot	Safety

Statistical Analysis Plan

REGiMMUNE Corporation

Protocol: RGI-2001-003

Figure Number and Title	Analysis Population
Figure 1.8 AST by Study Day Scatter Plot	Safety
Figure 1.9 ALT by Study Day Scatter Plot	Safety
Figure 1.10 GGT by Study Day Scatter Plot	Safety
Figure 1.11 Albumin by Study Day Scatter Plot	Safety
Figure 1.12 Total Bilirubin by Study Day Scatter Plot	Safety
Figure 1.13 Direct Bilirubin by Study Day Scatter Plot	Safety
Figure 2.1 GvHD-free Survival (Keystone Grades II-IV)	Safety
Figure 2.2 GvHD-free Survival (Keystone Grades III-IV)	Safety
Figure 2.3 Overall Survival (OS)	Safety
Figure 2.4 Non-Relapse Mortality (NRM)	Safety
Figure 2.5 Relapse Free-Survival (RFS)	Safety
Figure 2.6 GvHD-free, relapse-free survival GRFS	Safety

Appendix A

Assignment of CTCAE grades for Laboratory values using CTCAE Version 5.0:

Parameter	CTCAE Term	Grade 1	Grade 2	Grade 3	Grade 4	Grade 5
ALT	Alanine aminotransferase increased	>ULN - 3.0 x ULN if baseline was normal; 1.5 - 3.0 x baseline if baseline was abnormal	>3.0 - 5.0 x ULN if baseline was normal; >3.0 - 5.0 x baseline if baseline was abnormal	>5.0 - 20.0 x ULN if baseline was normal; >5.0 - 20.0 x baseline if baseline was abnormal	>20.0 x ULN if baseline was normal; >20.0 x baseline if baseline was abnormal	-
ALP	Alkaline phosphatase increased	>ULN - 2.5 x ULN if baseline was normal; 2.0 - 2.5 x baseline if baseline was abnormal	>2.5 - 5.0 x ULN if baseline was normal; >2.5 - 5.0 x baseline if baseline was abnormal	>5.0 - 20.0 x ULN if baseline was normal; >5.0 - 20.0 x baseline if baseline was abnormal	>20.0 x ULN if baseline was normal; >20.0 x baseline if baseline was abnormal	-
AST	Aspartate aminotransferase increased	>ULN - 3.0 x ULN if baseline was normal; 1.5 - 3.0 x baseline if baseline was abnormal	>3.0 - 5.0 x ULN if baseline was normal; >3.0 - 5.0 x baseline if baseline was abnormal	>5.0 - 20.0 x ULN if baseline was normal; >5.0 - 20.0 x baseline if baseline was abnormal	>20.0 x ULN if baseline was normal; >20.0 x baseline if baseline was abnormal	-
Total Bilirubin	Blood bilirubin increased	>ULN - 1.5 x ULN if baseline was normal; > 1.0 - 1.5 x baseline if baseline was abnormal	>1.5 - 3.0 x ULN if baseline was normal; >1.5 - 3.0 x baseline if baseline was abnormal	>3.0 - 10.0 x ULN if baseline was normal; >3.0 - 10.0 x baseline if baseline was abnormal	>10.0 x ULN if baseline was normal; >10.0 x baseline if baseline was abnormal	-
Direct Bilirubin	Blood bilirubin increased	>ULN - 1.5 x ULN if baseline was normal; > 1.0 - 1.5 x baseline if	>1.5 - 3.0 x ULN if baseline was normal; >1.5 - 3.0 x baseline if	>3.0 - 10.0 x ULN if baseline was normal; >3.0 - 10.0 x baseline if	>10.0 x ULN if baseline was normal; >10.0 x baseline if	-

Statistical Analysis Plan

REGiMMUNE Corporation

Protocol: RGI-2001-003

Parameter	CTCAE Term	Grade 1	Grade 2	Grade 3	Grade 4	Grade 5
		baseline was abnormal	baseline was abnormal	baseline was abnormal		
BUN	Blood Urea Nitrogen Increased	23 – 26	27 – 31	> 31	-	-
Cholesterol	Cholesterol high	>ULN - 300 mg/dL; >ULN - 7.75 mmol/L	>300 - 400 mg/dL; >7.75 - 10.34 mmol/L	>400 - 500 mg/dL; >10.34 - 12.92 mmol/L	>500 mg/dL; >12.92 mmol/L	-
Creatine Phosphokinase (CPK)	CPK increased	>ULN - 2.5 x ULN	>2.5 x ULN - 5 x ULN	>5 x ULN - 10 x ULN	>10 x ULN	-
Creatinine	Creatinine increased	>ULN - 1.5 x ULN	>1.5 - 3.0 x baseline; >1.5 - 3.0 x ULN	>3.0 x baseline; >3.0 - 6.0 x ULN	>6.0 x ULN	-
Fibrinogen	Fibrinogen decreased	<1.0 - 0.75 x LLN; if abnormal, <25% decrease from baseline	<0.75 - 0.5 x LLN; if abnormal, 25 - <50% decrease from baseline	<0.5 - 0.25 x LLN; if abnormal, 50 - <75% decrease from baseline	<0.25 x LLN; if abnormal, 75% decrease from baseline; absolute value <50 mg/dL	-
Hemoglobin	Hemoglobin increased	Increase in >0 - 2 g/dL	Increase in >2 - 4 g/dL	Increase in >4 g/dL	-	-
Hemoglobin	Anemia	Hemoglobin (Hgb) <LLN - 10.0 g/dL; <LLN - 6.2 mmol/L; <LLN - 100 g/L	Hgb <10.0 - 8.0 g/dL; <6.2 - 4.9 mmol/L; <100 - 80g/L	Hgb <8.0 g/dL; <4.9 mmol/L; <80 g/L;	-	-
Lymphocyte	Lymphocyte count decreased	<LLN - 800/mm ³ ; <LLN - 0.8 x 10e9/L	<800 - 500/mm ³ ; <0.8 - 0.5 x 10e9 /L	<500 - 200/mm ³ ; <0.5 - 0.2 x 10e9 /L	<200/mm ³ ; <0.2 x 10e9 /L	-
Lymphocyte	Lymphocyte count increased	-	>4000/mm ³ - 20,000/mm ³	>20,000/mm ³	-	-

Statistical Analysis Plan

REGiMMUNE Corporation

Protocol: RGI-2001-003

Parameter	CTCAE Term	Grade 1	Grade 2	Grade 3	Grade 4	Grade 5
Neutrophil	Neutrophil count decreased	<LLN - 1500/mm ³ ; <LLN - 1.5 x 10e9 /L	<1500 - 1000/mm ³ ; <1.5 - 1.0 x 10e9 /L	<1000 - 500/mm ³ ; <1.0 - 0.5 x 10e9 /L	<500/mm ³ ; <0.5 x 10e9 /L	-
Platelet	Platelet count decreased	<LLN - 75,000/mm ³ ; <LLN - 75.0 x 10e9 /L	<75,000 - 50,000/mm ³ ; <75.0 - 50.0 x 10e9 /L	<50,000 - 25,000/mm ³ ; <50.0 - 25.0 x 10e9 /L	<25,000/mm ³ ; <25.0 x 10e9 /L	-
Leukocytes	White blood cell decreased	<LLN - 3000/mm ³ ; <LLN - 3.0 x 10e9 /L	<3000 - 2000/mm ³ ; <3.0 - 2.0 x 10e9 /L	<2000 - 1000/mm ³ ; <2.0 - 1.0 x 10e9 /L	<1000/mm ³ ; <1.0 x 10e9 /L	-
Leukocytes	Leukocytosis	-	-	>100,000/mm ³	-	-
Mag-nesium	Hyper-magnesemia	>ULN - 3.0 mg/dL; >ULN - 1.23 mmol/L	-	>3.0 - 8.0 mg/dL; >1.23 - 3.30 mmol/L	>8.0 mg/dL; >3.30 mmol/L;	
Triglycerides	Hyper-triglyceridemia	150 mg/dL - 300 mg/dL; 1.71 mmol/L - 3.42 mmol/L	>300 mg/dL - 500 mg/dL; >3.42 mmol/L - 5.7 mmol/L	>500 mg/dL - 1000 mg/dL; >5.7 mmol/L - 11.4 mmol/L	>1000 mg/dL; >11.4 mmol/L;	
Albumin	Hypo-albuminemia	<LLN - 3 g/dL; <LLN - 30 g/L	<3 - 2 g/dL; <30 - 20 g/L	<2 g/dL; <20 g/L		
Blood Glucose	Hypoglycemia	<LLN - 55 mg/dL; <LLN - 3.0 mmol/L	<55 - 40 mg/dL; <3.0 - 2.2 mmol/L	<40 - 30 mg/dL; <2.2 - 1.7 mmol/L	<30 mg/dL; <1.7 mmol/L;	
Mag-nesium	Hypo-magnesemia	<LLN - 1.2 mg/dL; <LLN - 0.5 mmol/L	<1.2 - 0.9 mg/dL; <0.5 - 0.4 mmol/L	<0.9 - 0.7 mg/dL; <0.4 - 0.3 mmol/L	<0.7 mg/dL; <0.3 mmol/L;	
GGT	GGT Increased	>ULN - 2.5 x ULN if baseline was normal; 2.0 - 2.5 x baseline if baseline was abnormal	>2.5 - 5.0 x ULN if baseline was normal; >2.5 - 5.0 x baseline if	>5.0 - 20.0 x ULN if baseline was normal; >5.0 - 20.0 x baseline if	>20.0 x ULN if baseline was normal; >20.0 x baseline if baseline was abnormal	

Parameter	CTCAE Term	Grade 1	Grade 2	Grade 3	Grade 4	Grade 5
			baseline was abnormal	baseline was abnormal

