### 6.1.1 Definition of Dose-limiting Toxicities

[figure not shown]
All subjects are expected to experience hematologic toxicity as part of the myeloablative alloHSCT procedure. Therefore, hematologic toxicities (e.g., leukopenia and thrombocytopenia) will not be useful measures of drug-induced toxicity, and DLTs are defined by non-hematologic toxicities.

The following DLT criteria apply to the Safety Run-in Phase of the study. A DLT is defined as any treatment-related AE that is not attributable to an extraneous cause (i.e., disease progression, preparatory regimen or HSCT infusion) and also excludes any signs and symptoms of GvHD. DLT is an adverse event occurring in the period of 30 days after the first dose of RGI-2001 administration, and meeting at least one of the following NCI CTC (Version 5.0) criteria:

- Grade 3+ infusion-related/cytokine release reactions
- Graft failure (as defined in Section 9.4.1.)
- Any Grade 4-5 non-hematological AE
- Delay in dosing by > 2 weeks due to treatment-related AE that is not attributable to an extraneous cause as defined above

Subjects who do not complete the DLT window for reasons other than toxicity may be replaced. Similarly, if a subject receives ≤ 50% of planned doses of RGI-2001 for reasons other than toxicity considered related to RGI-2001, this subject may be replaced.

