4.0 STATISTICAL METHODS OF ANALYSIS

4.1 Statistical Considerations

Continuous variables will be summarized (based on the subjects with non-missing values) by the number of subjects (n), mean, standard deviation (SD), median, minimum value, and maximum value. Mean and median will be accurate to one more digit decimal point than the original data, and standard deviation will be accurate to two more-digit decimal points than the original data, and the decimal points of the maximum and minimum values will be the same as the original data.

Categorical variables will be summarized (based on the subjects with non-missing values) by the frequency (count and percent) of subjects falling within the category. The denominator for all

percentages, unless otherwise specified, will be the number of subjects in the specified analysis population.

Point estimates of time-to-event outcomes will be obtained using either Kaplan-Meier or cumulative incidence estimates, depending on whether endpoints have competing risks. Survival at a variety of specific endpoints will be presented in the tabled output, including Day 100 (i.e., primary endpoint for aGvHD) and Day 365 (i.e., EOS). In addition (if applicable), the median length of survival (in days) will be presented. Furthermore, listed data for all time-to-event outcomes will be provided.

Regarding the time-to-event estimates, the time between begin and end dates for events and censors is important in the calculation. If either of the dates are invalid, then the 1st will be assumed (for missing day) and/or January will be assumed (for missing month). Assumptions will only be incorporated into the analysis if calculation of time does not result in a negative number of days. If negative, the subject will not be used in the analysis. If assumptions are needed, they will be flagged in the listings.

Almost all data from the electronic case report form (eCRF) will be listed. For example, time (mm:hh) will be excluded from almost all listings except for the PK and PD listings. From lab listings, the lab name and the original value for the dose in the units collected on the eCRF will be excluded and replaced with the value in SI units. Also a few variables collected on the AE eCRF and other eCRFs will be excluded from the listings.

Baseline will be defined as the last assessment completed prior to the administration of the study drug (Day 0, which corresponds with date of transplant).

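### SAP Appendix A grades a rise in hemoglobin with no upper-limit condition and no stated reference value, so recovery within the normal range after conditioning can be graded up to Grade 3

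*SAP*

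**What the plan says.** SAP Appendix A has two rows for hemoglobin. The anemia row grades by level: Grade 3 below 8.0 g/dL, Grade 2 from 8.0 to below 10.0, and Grade 1 from 10.0 to below the lower limit of normal (LLN). The 'Hemoglobin increased' row grades by change only: Grade 1 is "Increase in >0 - 2 g/dL", Grade 2 is "Increase in >2 - 4 g/dL" and Grade 3 is "Increase in >4 g/dL". There is no Grade 4 or 5. The row names neither a ULN nor a starting value.

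On baseline, SAP 4.1 states: "Baseline will be defined as the last assessment completed prior to the administration of the study drug". It identifies that administration with Day 0, the transplant date. SAP Table 10.0 repeats the definition and gives change from baseline as the current value minus the baseline value. The protocol's Schedule of Assessments places a hematology sample on Day 0 before the transplant.

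On use of the grades, SAP 9.6 says that for selected parameters "grading will be assigned using CTCAE version 5.0 guidelines (Appendix A) and summary tables will be provided". It does not list those parameters. The hematology table named by grade is Table 14.3.5.7, "Hematology Laboratory Values Worsening from Baseline Grade 0-2 to Grade 3-4 During the Treatment-Emergent Period". Table 14.3.5.9 gives hematology shifts from baseline without stating the scale.

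**The concern.** Every other upward row in Appendix A has an anchor in at least one grade. The rows for ALT, ALP, AST, both bilirubins, GGT, CPK, creatinine, cholesterol and high magnesium refer to the ULN. The rows for BUN, triglycerides, high lymphocytes and leukocytosis use absolute levels. 'Hemoglobin increased' has neither, so on its face any rise above zero is graded.

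The population makes this matter. The Day 0 sample normally follows the preparatory regimen. Protocol 6.1.1 says: "All subjects are expected to experience hematologic toxicity as part of the myeloablative alloHSCT procedure". Protocol 8.8 permits transfusions as supportive care. A hemoglobin that is low on Day 0 and later rises is a plausible and welcome course, and the row would score it as a graded abnormality.

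Laboratory values are part of the primary safety endpoint (SAP 1.1). This SAP also leaves the comparison with registry controls to a separate document (SAP 8.0), so these tables carry no control column against which the effect would show itself.

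**Working it through.** The plan states no figure to reproduce here. The check is to apply the two hemoglobin rows as written.

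**Inputs from the documents.** The grade cut-offs are those of Appendix A. The increase is taken as the later value minus baseline, as SAP Table 10.0 defines change. This is a reading, because the row itself gives no reference.

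**Assumptions, not in the documents.** Baseline is 7.5 to 10.0 g/dL and later values are 8.1 to 14.5 g/dL. The local normal range is 12 to 16 or 13.5 to 17.5 g/dL.

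**Step 1: grades as written, and with a ULN anchor.** The last column measures the increase above the greater of the ULN and baseline.

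| Baseline | Later | Increase | 'Increased' grade as written | Anemia grade, baseline to later | 'Increased' grade with ULN anchor |
|---|---|---|---|---|---|
| 8.0 | 8.1 | 0.1 | 1 | 2 to 2 | 0 |
| 8.0 | 9.0 | 1.0 | 1 | 2 to 2 | 0 |
| 8.0 | 11.0 | 3.0 | 2 | 2 to 1 | 0 |
| 8.0 | 12.1 | 4.1 | 3 | 2 to 0 (LLN 12) or 1 (LLN 13.5) | 0 |
| 7.5 | 12.0 | 4.5 | 3 | 3 to 0 (LLN 12) or 1 (LLN 13.5) | 0 |
| 10.0 | 14.5 | 4.5 | 3 | 1 to 0 | 0 |

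In the second line one value, 9.0 g/dL, is both Grade 2 anemia and Grade 1 'increased'.

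**Step 2: where Grade 3 starts.** The threshold is baseline + 4. For baselines of 7.5, 8.0, 8.5, 9.0 and 10.0 it lies at 11.5, 12.0, 12.5, 13.0 and 14.0 g/dL, all below either assumed ULN. A value within range can reach Grade 3 whenever baseline + 4 is below the ULN. That means a baseline below 16 − 4 = 12.0 or 17.5 − 4 = 13.5 g/dL.

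**Step 3: what enters Table 14.3.5.7.** The table needs baseline Grade 0-2 and a later Grade 3-4. The answer depends on how it is built:

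- By term: the baseline grade for 'increased' is always 0, so every rise above 4 g/dL in the window enters.
- By parameter, taking the worst grade in either direction: 8.0 to 12.1 runs from Grade 2 to Grade 3 and enters. A change of 7.5 to 12.0 starts at Grade 3 anemia and does not.
- Rises of 4 g/dL or less cannot enter as increases under either build, because they are Grade 1 or 2.

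**Step 4: the window.** The SAP defines treatment-emergent for adverse events as up to 30 days after the last dose (SAP 9.1). If the laboratory tables use the same window and the last dose is on Day 35, it ends on Day 35 + 30 = 65, or Day 66 with the one-day dosing window. The Day 60 visit falls inside it. Later recovery does not count.

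**The case against.** The strongest reply has four parts.

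- **The row never says 'from baseline'.** This is correct. The demonstrable gap is an unstated reference value. Baseline is the natural reading because the SAP defines no other reference for change, but it remains a reading. If the Day 0 sample is missing, baseline also falls back to an earlier assessment that may precede conditioning.
- **Appendix A claims to follow CTCAE version 5.0, so an added ULN condition may depart from the standard.** Whether the row matches the published text cannot be checked from the documents, and nothing here relies on it. The point rests on what the row does in this population.
- **Hemoglobin is not named as a selected parameter, and the table shells are in a separate document.** This is also correct. The inference is still strong. SAP 9.6 gives the selected parameters figures over time, hemoglobin has one (Figure 1.1), and it has two rows in Appendix A.
- **Other outputs show the recovery.** Table 14.3.5.2, Figure 1.1 and the hematology listing let a careful reader see it. This stands, and it limits the harm.

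A reader might infer more than the documents support:

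- *That most subjects would be tabulated with a graded hemoglobin increase.* The documents give no hemoglobin level, mean rise or standard deviation, so any percentage would come wholly from assumed values. Protocol 6.1.1 expects hematologic toxicity, but its examples are leukopenia and thrombocytopenia. It does not say that subjects are anemic on Day 0.
- *That Grades 1 to 3 are all reported.* Only Grade 3 can enter the one hematology table named by grade. Table 14.3.5.9 could equally use the low/normal/high scale that SAP 9.6 also describes.
- *That these grades become adverse events or affect trial decisions.* Protocol 10.2.1 says that not every laboratory abnormality is an adverse event. The dose-limiting toxicity definition (Protocol 6.1.1), the Grade 3 dose-change rule for the expansion phase (8.10.2) and the suspension rules (12.4) do not draw on this row.

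**Conclusion.** The point holds in a limited form. As written, the row has no ULN condition and no reference value. Read against the SAP's baseline, it can grade transfusion or marrow recovery within the normal range up to Grade 3. A rise above 4 g/dL from a baseline of 8.0 g/dL could then be counted in Table 14.3.5.7 as worsening while the anemia row shows improvement.

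The conclusion assumes that the increase is taken from baseline, that hemoglobin is among the selected parameters, and that Table 14.3.5.7 is built by term or by worst grade in either direction. The number of subjects affected cannot be derived from the documents. The consequence is a potentially misleading entry in the laboratory safety tables and nothing beyond them. It is worth correcting because the correction is small.

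**What to change.** 1. In Appendix A, grade 'Hemoglobin increased' only when the post-baseline value exceeds the local ULN. Measure the increase above the ULN, or above baseline if baseline exceeds the ULN. Otherwise assign Grade 0. The cut-offs of 0, 2 and 4 g/dL can stay. All pairs in the table above then score Grade 0.
2. Build Tables 14.3.5.7 and 14.3.5.9 by term and direction, and say so, so that recovery from anemia is not counted as worsening. State whether Table 14.3.5.9 uses CTCAE grades.

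The cost is one line in Appendix A and in the grading program, and a footnote noting that a ULN condition was added to the row. The local normal ranges are already used to flag out-of-range values (SAP 9.6), so no new data are needed.
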